13.0 POTENTIAL BENEFITS TO PARTICIPANTS

No direct benefit

14.0 DATA MANAGEMENT AND CONFIDENTIALITY

STU#: 00208846

14.1 All collected data will be stored on a locked and secured Northwestern Memorial computer located in the Center for Comprehensive Gynecology. Only study team will have access to the data. Photos will be taken in the OR. Images will be collected after surgery and de-identified then uploaded into ImageJ and Photoshop for analysis. Only study team will conduct data analysis.

14.2 **Statistical procedures:** Images pixelation intensity will be assessed in ImageJ and Photoshop. A paired t-test will be used to assess a patient's ovary with pathology and the ovary without pathology to determine whether there are any differences in ICG intensity.

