2.5 Drug interactions

Listed drug interactions include preparations containing sodium bisulfite which reduce the absorption peak of ICG (KARL STORZ Endoscopy - America, 2016)

3.0 STUDY ENDPOINTS:

3.1 Primary Objectives:

3.1.1 To assess the feasibility of using intravenous ICG to characterize the vascular perfusion of ovaries.

3.1.2 To utilize infrared light to image and detect adnexal ICG uptake.

STU#: 00208846

3.1.3 To qualitatively assess ovarian perfusion after ICG administration.

3.1.4 To quantitatively assess ovarian perfusion after ICG administration by analyzing the intensity of fluorescence on intraoperative imaging.

3.2 Secondary Objectives:

3.2.2 To qualitatively and quantitatively compare and contrast adnexal ICG uptake in the presence and absence of adnexal pathology.

4.0 STUDY INTERVENTION(S) / INVESTIGATIONAL AGENT(S):

ICG will be injected intravenously to assess ovarian perfusion in the presence or absence (control) of pathology. Near infrared fluorescence imaging will be used to illuminate the ICG. The extent of perfusion will be determined using digital imaging software.

ICG will be stored at the NM Investigational Pharmacy and administered intravenously by the anesthesiologist at the direction of the surgeon during surgical procedure.

5.0 PROCEDURES INVOLVED:

5.1.1 Patients who are scheduled to undergo surgery at Northwestern Memorial Hospital will be approached for recruitment of the study at their preoperative visit in the Center for Comprehensive Gynecology clinic. Research coordinator will review consent form with potential participant. Ample time will be left for participant questions and comprehension

5.2.1 The screening procedures include:

Informed consent: will be obtained for all potentially eligible participants. Once consented we will review subject eligibility referring to inclusion and exclusion criteria.

5.2.2 Medical History: Complete medical, surgical, gynecologic and obstetrical history, medications, allergies, social and family history.

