5.4.1 Data Analysis

Images will be stored on locked Northwestern Memorial computers which only the study team will be able to access. Once imaging data is complete, study team will collect basic intensity quantification utilizing both *ImageJ* and Photoshop software.

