7.0 STUDY TIMELINES

7.1 Participants will be consented and enrolled at their pre-operative appointment

7.2 Study duration includes the time during ICG administration, visualization and imaging. Because this will be performed intraoperatively during standard survey of the abdomen and pelvis no surgical delays will be incurred. No other procedures or visits are necessary for participants in this study. If a participant seeks further treatment in the future at the Center for Comprehensive Gynecology, study coordinator will approach previous participant and consent them to participate in the study again.

7.3 Once imaging data is complete, study team will collect basic intensity quantification using *ImageJ* or *Photoshop*

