16.0 PROVISIONS TO PROTECT THE PRIVACY INTERESTS OF PARTICIPANTS

All participants will have ample time to discuss any questions, concerns or comments about the study. Participants may also contact study coordinator after pre-operative visit if any other questions arise. Participant images will be de-identified and screening data will be secured on a locked Northwestern Memorial computer.

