18.0 QUALIFICATIONS TO CONDUCT RESEARCH AND RESOURCES AVAILABLE

The Center for Comprehensive Gynecology sees a number of pre-operative patients presenting for gynecologic surgery. Both PI and Co-PI have extensive research and surgical experience. Entire study team is CITI Biomedical Research Trained. Study team collaborated on the study protocol and each member is well versed in the study procedures and their study duties.

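### Section 14.1 de-identifies the images but does not mask whoever measures them to side or pathology, so the one named test is open to reader bias

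*Protocol*

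**What the plan says.** Section 14.1 sets out the handling of the images. Photographs are taken in the operating room, and then "Images will be collected after surgery and de-identified then uploaded into ImageJ and Photoshop for analysis". The same section adds "Only study team will conduct data analysis". Section 5.4.1 gives the measurement to the same group: "study team will collect basic intensity quantification utilizing both *ImageJ* and Photoshop software". Section 7.3 repeats this, but offers the two programs as alternatives.

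Section 14.2 states the analysis: "A paired t-test will be used to assess a patient's ovary with pathology and the ovary without pathology". No other test is named. The comparison serves the secondary objective (3.2.2).

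Section 16.0 lists de-identification among the privacy provisions: "Participant images will be de-identified and screening data will be secured on a locked Northwestern Memorial computer". No section says that the person measuring is kept unaware of side or pathology, names that person, or gives a rule for the area to be measured.

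**The concern.** De-identification hides whose ovary it is. It does not hide which ovary is the diseased one, and that is the label the paired test contrasts.

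Three features make a lean in the reading plausible. First, the study team takes a full history at screening (5.2.2: "Complete medical, surgical, gynecologic and obstetrical history, medications, allergies, social and family history"), so members of the permitted group will know the clinical picture. Second, the measurement is described only as basic, with no area rule and with two programs required in one place and offered as alternatives in another. Third, the background in section 2.2 supplies an expected direction: it cites low flow and a high resistance index in ovaries with endometriomas.

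Pairing does not protect against this. It cancels what the two ovaries of one patient share. A reader who treats diseased and healthy ovaries differently shifts every difference the same way. At stake is an apparent perfusion deficit that comes from the reading. Section 9.0 wants this pilot to prepare the ground for later studies, so such a result could be carried forward. The qualitative assessment (3.1.3, listed as primary) also has no stated masking.

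**Working it through.** **Setting the sections side by side**

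| Step | Where | Stated | Not stated |
|---|---|---|---|
| Capture | 14.1 | Photographs in the operating room | Masking (hardly possible here) |
| Preparation | 14.1, 16.0 | De-identified, as a privacy measure | Coding of side or diagnosis |
| Measurement | 5.4.1, 7.3, 14.1 | By the study team | Which member; area rule; masking |
| Timing | 7.4 | Analysis as images arrive | A locked read before comparison |
| Test | 14.2 | Paired t-test by pathology status | – |

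**Illustration of what a bias would do**

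The protocol gives no alpha, power, SD, measurement error or number of patients with one diseased and one healthy ovary. It states only 30 participants (9.0). There is no figure to reproduce, and every input below is an assumption.

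- Usable pairs: n = 15.
- Test: two-sided 5%, critical value t(0.975, 14) = 2.145.
- True difference: zero.
- Reader bias: the diseased ovary is read 5% or 10% too low, so the shift on the log scale is log(0.95) = −0.0513 or log(0.90) = −0.1054. The log scale is a convenience; section 14.2 does not specify it.
- SD of the paired log-ratio: 0.20, 0.28 or 0.50.

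Noncentrality λ = |shift| / SD × √n. The false-positive rate is P(|T′| > 2.145), with T′ noncentral t on 14 degrees of freedom. For example, a 10% bias at SD 0.20 gives λ = 0.1054 / 0.20 × √15 = 2.04.

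| SD | 5% bias: λ | rate | 10% bias: λ | rate |
|---|---|---|---|---|
| 0.20 | 0.99 | 15.3% | 2.04 | 47.6% |
| 0.28 | 0.71 | 10.2% | 1.46 | 27.4% |
| 0.50 | 0.40 | 6.6% | 0.82 | 11.9% |

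More pairs make the inflation worse, because the bias stays while the standard error shrinks: with 30 pairs and SD 0.28 the rates are 16.3% and 51.3%.

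**What partial masking would buy**

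Here the bias is expressed in SDs of the paired difference, which does not depend on the scale. With 15 pairs, halving a bias of 0.3 SD lowers the rate from 19.2% to 8.4%; halving a bias of 0.5 SD lowers it from 43.8% to 14.7%. Only complete removal returns it to 5%.

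**The case against.** The strongest reply is that this is an omission of the kind that an SAP or imaging manual fills, and that the sentence about the study team only restricts access to data; it would stay true after the fix. Part of this stands. The sentence does not require an unmasked read, and a reading manual not shown may contain the missing rules. But how images are prepared before measurement, and by which group, is study conduct that section 14.1 already sets out. As it stands, that chain has a de-identification step and no masking step.

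A reader might infer that the operating surgeon, knowing the diagnosis, measures the images. The document does not support that. Section 18.0 says only "Both PI and Co-PI have extensive research and surgical experience"; it does not say that they read the images, and a research coordinator also belongs to the team. De-identification may itself give partial protection if the reader was not at the operation. Nor does the protocol say that frames or areas are picked by hand.

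It is also fair to object that masking cannot undo what is fixed at capture, such as timing, angle or distance, and that a cyst or endometrioma may be visible in the image. Both stand. So does the point about cost: matched white-light frames or frames at set times might need a capture procedure that the protocol does not describe, so the remedy should not depend on them.

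Finally, the contrast is secondary in a pilot, and the main feasibility objective does not rest on it. This lowers the stakes but does not justify leaving a cheap safeguard out.

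**Conclusion.** The point holds in a limited form. The plan as written leaves its only named test open to reader bias, because nothing masks the person measuring to side or pathology. That is a gap in protection. It is not evidence that a biased read will occur.

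The size is unknown. The range of about 7% to 48%, against a nominal 5%, rests wholly on assumed pairs, SD and bias. It shows the direction of the problem and its sensitivity to small biases, and should not be quoted as an estimate for this trial. It would also go too far to say that the team could remove the bias altogether: visible lesions and unmasked capture set a limit. The change is worth making before images are read, in proportion to a secondary objective of a feasibility study.

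**What to change.** In section 14.1, extend the existing de-identification step:

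- Replace patient, side and diagnosis labels with a random code, and present all ovary images in random order.
- Have an existing team member who was not at that operation measure them, using one area rule set in advance.
- Merge pathology status only after the intensities are locked.
- State that masking is incomplete where the lesion can be seen, and that capture in the operating room is unmasked.

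Adjust section 7.4, which has images analysed as they arrive, so that the comparison is run after the locked read. If a reading manual or SAP already contains these rules, a cross-reference in 14.1 is enough.

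The cost is a short addition to 14.1, an edit to 7.4, some file handling, and reading in batches. It needs no extra reader and adds no burden for participants.

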15.0 PROVISIONS TO MONITOR THE DATA TO ENSURE THE SAFETY OF PARTICIPANTS

All patients will be closely monitored by physician and nursing staff in the operating room and postoperative recovery area for the full duration of action of the active medication. ICG is considered a safe, well-studied medication.

16.0 PROVISIONS TO PROTECT THE PRIVACY INTERESTS OF PARTICIPANTS

All participants will have ample time to discuss any questions, concerns or comments about the study. Participants may also contact study coordinator after pre-operative visit if any other questions arise. Participant images will be de-identified and screening data will be secured on a locked Northwestern Memorial computer.

17.0 ECONOMIC BURDEN TO PARTICIPANTS

Participants who elect to participate in this study, may participate with no additional charges.

18.0 QUALIFICATIONS TO CONDUCT RESEARCH AND RESOURCES AVAILABLE

The Center for Comprehensive Gynecology sees a number of pre-operative patients presenting for gynecologic surgery. Both PI and Co-PI have extensive research and surgical experience. Entire study team is CITI Biomedical Research Trained. Study team collaborated on the study protocol and each member is well versed in the study procedures and their study duties.
